#### 10. Risks and benefits

#### 10.1. Potential risks

Because it is an observational study of marketed products, there are no additional risks through participating in the study.

In the study, the products will be used in accordance with their labeling, therefore no risks different from those normally associated with standard clinical practice of the device are foreseen.

#### 10.2. Potential benefits

There are no direct benefits for the subject arising from participation in the study. However, the information obtained through this study may result in an improvement of the knowledge of the subject population with atrial fibrillation and of the procedure to follow in cryoballoon ablation of these subjects. On the other hand, the information extracted from the usual processes at the participating sites can significantly help to standardize the suitability of treatment depending on the different clinical profiles.

#### 10.3. Risk-benefit rationale

Section not applicable since there are no additional risks from participating in the registry or direct benefits for the subject arising from his/her participation in it.

#### 11. Adverse Events Assessment

#### 11.1. Definitions/Classification

The products used have the CE mark and are used under the authorized indications for use according to their label. However, it is the investigator's responsibility to comply with any requirements for the reporting of Adverse Events (AE) as required by the Clinical Investigation Plan, by local legislation, and the specific requirements of each EC.

An adverse event (AE) is any unfavorable medical incidence, unexpected disease or lesion, or any unfavorable clinical sign (including abnormal laboratory findings) in subjects, users or other persons, whether this is related or not to the medical device, and whether this is envisaged or not in the instructions for use.

A USADE is defined as any SAE relating to health, safety or any potentially fatal problem or death, caused by a device or associated therewith, that has not been identified previously in nature, intensity or level of incidence in the investigation plan, in the instructions for use or in the leaflet.

The incorrect functioning of the device is defined as the non-compliance with the specifications for use of the device or its functioning in a different way to the one specified for the known indication.

## 11.2. Adverse Event and Device Defficiency reporting

The investigators of this registry will report any deficiencies/malfunction and any adverse events related to the medical device through the regular channel from the vigilance system. As part of Medtronic's continual post-marketing safety assessment, Medtronic will evaluate those experiences and events and will produce monitoring reports for the local competent authorities as required.

The investigator must notify the sponsor or its representative and the reviewing EC of any unexpected adverse event of the device, within 24 hours from awareness date.

In this registry, the adverse events will be reported through the eCRF. The investigator must enter all the information on the eCRF as soon as possible and before 10 calendar days from awareness date of the event, as long as the regulatory authorities do not require stricter timelines.

The following adverse events will be collected in this registry:

- Unanticipated Serious Adverse Device Events (USADE):
- All adverse events that lead to death.
- All adverse events related to the procedure (up to 30 days post-procedure), such as (non-exhaustive list):
  - Access site complications:
    - Arteriovenous fistula
    - Pseudoaneurysm
  - Endocarditis
  - Cardiac damage (including myocardial infarction)
  - Embolic complications (including stroke)
  - Tamponade (associated or not to urgent surgery)
  - Hemorrhage requiring transfusion
  - Temporal Paralysis of the phrenic nerve

Version 1.0 11/APR/2016

- Persistent Paralysis of the phrenic nerve
- Pulmonary vein stenosis
- Intense cephalea
- Hemoptysis
- Gastroparesis
- Mitral valve tearing
- Temporary STU elevation

Note: Early recurrences of AF/AFL/AT after the cryoablation process are to be expected. If these recurrences, which may require hospitalization of the subject or extension of his/her hospitalization, are within the "blanking" period, they will not be considered greater complications than the cryoablation procedure.

Note 2: temporal paralysis of phrenic nerve is defined as decrease in diaphragmatic excursion resolved prior to end of procedure. Detection of phrenic nerve damage prior to detectable decrease in diaphragmatic excursion during procedure will not be considered as AEs.

- All adverse events related to AF not related to the procedure (that appear after 30 days, throughout the study), which could be (non-exhaustive list):
  - Cardiovascular death
  - Systemic embolism
  - Congestive heart failure
  - Hemorrhagic events without stroke
  - Myocardial infarction
  - Stroke
  - Arrhythmia: atrial flutter or inappropriate sinus tachycardia or sinus dysfunction after the blanking period
  - Recurrence of AF or left flutter after the blanking period

Note: The cases of recurrence of AF and the hospitalizations arising from AF will be collected in the adverse event form even though they will be processed as part of the analysis of the efficacy and not safety variables.

The investigator has to specify on the eCRF whether an adverse event can be deemed to be serious or not. If the adverse event meets any of the following criteria, it is considered a serious adverse event (SAE):

- Led to death
- Caused serious deterioration in the subject's health that has:
  - a) resulted in a life-threatening illness or injury, or
  - b) resulted in a permanent impairment of a body structure or a body function, or
  - c) required in-subject hospitalization or prolongation of existing hospitalization, or
  - d) resulted in medical or surgical intervention to prevent life threatening illness or injury or permanent impairment to a body structure or a body function.

Note: Planned hospitalization for a pre-existing condition is not considered a serious adverse event.

Note 2: Hospitalization is defined as patient staying overnight at the hospital (more than 24h)

The investigator also has to evaluate on the eCRF whether there is a reasonable possibility that the device may have caused or contributed to an AE. The factors that could be considered are time relationships, biological plausibility, the association (or lack of association) with the underlying disease and the presence (or absence) of a more likely cause. If an adverse event is classiffied as potentially related to the device this should be also notififed following the regular communication channels of the vigilance system.

All the data collected relating to adverse events will be reviewed remotely to ensure the correct reporting and classification of the event. In the event of having doubts about the classification and relationship with the device established by the investigator, the Scientific Committee will be consulted.

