#### 5.1.2. Secondary Objectives

- Description of the profile of subjects who undergo this type of procedure (demographic factors, cardiovascular risk factors, medication, physical activity, sleep apnea, alcohol, smoking, chronic pulmonary disease, obesity, etc.).
- To evaluate the acute efficacy of the procedure: complete isolation of the pulmonary veins demonstrated by the successful electrical disconnection of the pulmonary veins in the cryoablation procedure.
- Description of the complications related to the procedure.
- To evaluate the use of healthcare resources which this cryoablation procedure entails.

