#### **Baseline procedure:**

- 1.- Demographic factors, cardiovascular risk factors (arterial hypertension, diabetes mellitus, dyslipidemia, smoking), physical activity, sleep apnea, body mass index.
- 2.- Evolution time of the arrhythmia, previous anti-arrhythmic treatments, previous cardioversions.
- 3.- Anatomical data arising from the imaging tests (left ventricular parameters, ejection fraction, ventricular wall thickness, diameter, area or volume of the left atrium, pulmonary vein drainage pattern, pulmonary vein diameters)
- 4.- Procedure variables: number of applications per vein, application time, registration of pulmonary vein potentials during the ablation, time to block the vein, minimum temperature reached, reheating time, isolation or not of the pulmonary vein, results of the adenosine test, procedure time, exposure time to radioscopy, complications, temperature details in each of the applications, temperature at the time of isolation.

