### **Descriptive analysis of the data**

The data repository is structured in 6 tables: Inclusion, Baseline data, Procedure, Follow-up, Adverse event and Study exit. Summary information will be provided on the variables collected in each of the tables.

Regarding dates, the time elapsed between dates or waiting times will be calculated as specified by the scientific coordinators of the study.

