## **Procedure**

The Procedure table contains technical information about the ablation procedure.

Continuous variables will be described using the statistics of central tendency (mean and median), dispersion (minimum, maximum, standard deviation and interquartile range) and shape (skewness and kurtosis). The number of valid cases and the number of cases with missing values will be reported. The continuous variables in this table are: Procedure date, TTE (sg), Minimum temperature ( $^{\circ}$ C), Application time (sg), Reheating time (sg), No. of balloons used, Total time of applications (min), Time total LA (min), Total procedure time (min), Total fluoroscopy time (min), Time to -30 degrees (sec), Rx Dose (PDA), Wait time (min), Contrast (ml), No. of cardioversions.

The categorical variables will be described by frequencies and percentages. The number of valid cases and the number of cases with missing values will be reported. The categorical variables contained in this table are: Study No., Previous Image, Image Type, Previous TEE (Transesophageal Echocardiography), General Anesthesia, Deep Sedation, Channeled Artery, No. of Diagnostic Catheters, Location of Diagnostic Catheters, Access, Assisted Transeptal, Assisted using, Phrenic nerve monitoring technique, Base rhythm, Applications, Vein, Application number, Potential visibility, Balloon size, Pulmonary vein isolation, Auriculogram, Protamine, Z-suture, Complications, Cardioversions, Number of cardioversions, Ablation ICT, Post-procedure antiarrhythmics, Antiarrhythmic type, Post-procedure anticoagulation, NACOs type, Base rhythm, Select type of Flutter, Catheter, Sheath, Specify.

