### **Adverse event**

The Adverse Event table contains clinical information regarding adverse events that occurred during patient follow-up. It is assumed that a patient may experience several (or none) adverse events during follow-up. Therefore, two types of descriptive analysis will be carried out, one using the number of patients as the unit of analysis (summarizing aspects such as the number of events per patient, maximum and minimum time between events, etc.) and another using the units of analysis as reported events (to summarize aspects such as the most frequent type of event, the most frequent level of severity, resolution of the events, etc.)

Continuous variables will be described using the statistics of central tendency (mean and median), dispersion (minimum, maximum, standard deviation and interquartile range) and shape (skewness and kurtosis). The number of valid cases and the number of cases with missing values will be reported. The continuous variables in this table are: Date of the adverse event, Date of knowledge of the EA, Date of resolution.

The categorical variables will be described by frequencies and percentages. The number of valid cases and the number of cases with missing values will be reported. The categorical variables contained in this table are: Type of event, event (s), Type of complications, event (s), Type of arrhythmia, Is the AE serious ?, Type of severity, Measures taken, Status of the event.

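### Section 11.2 has no registry class for a non-fatal, anticipated procedure-related event first appearing after day 30, and neither the complications objective nor the SAP states the 30-day limit

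*Protocol*

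**What the plan says.** Protocol section 11.2 lists the adverse events that the registry collects, in four classes. Two have no time limit: unanticipated serious adverse device events (USADE) and events leading to death. The third is "All adverse events related to the procedure (up to 30 days post-procedure), such as (non-exhaustive list", with named types that include pulmonary vein stenosis, gastroparesis and embolic complications. The fourth is "All adverse events related to AF not related to the procedure (that appear after 30 days, throughout the study", with examples such as stroke, systemic embolism and myocardial infarction. The section also asks the investigator to judge "whether there is a reasonable possibility that the device may have caused or contributed to an AE", and it sends device-related events to the vigilance system.

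The secondary objective in section 5.1.2 is "Description of the complications related to the procedure", with no time window. The SAP section on adverse events opens: "The Adverse Event table contains clinical information regarding adverse events that occurred during patient follow-up". It gives no 30-day limit. Nor does the SAP section on statistical models, which leaves the analyses of the secondary objectives to variables that the study coordinators will designate.

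Complications are also recorded with the procedure data. Protocol section 9.1 names "exposure time to radioscopy, complications, temperature details in each of the applications" among the procedure variables, and the SAP Procedure section lists "Complications, Cardioversions, Number of cardioversions". On where data are held, the SAP says: "The data repository is structured in 6 tables: Inclusion, Baseline data, Procedure, Follow-up, Adverse event and Study exit".

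**The concern.** The third class ends at day 30. The fourth starts there but excludes anything related to the procedure. A procedure-related event that first appears on day 31 or later therefore seems to fall between them, unless it is fatal or a USADE.

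The stake is a stated secondary objective. Section 11.2 carries a 30-day rule for procedural complications, while the objective and the SAP are worded as if the description covered all of follow-up. If sites apply the rule as written, late procedural complications are either left out or entered in a class whose wording says they are not procedural. The resulting complication figure would then be read as covering more time than it does.

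**Working it through.** The plan gives no complication rate or target, so there is no figure to reproduce. The check is whether each kind of procedure-related event has a class.

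**Step 1. Test the event in question against each class.** The USADE definition is in section 11.1; the rest are in section 11.2.

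| Class | Condition for entry | Late, non-fatal, anticipated, procedure-related event |
|---|---|---|
| USADE | serious, device-associated, not previously identified | excluded: anticipated |
| Fatal | leads to death | excluded: non-fatal |
| Procedure-related | up to day 30 | excluded: late |
| AF-related | after day 30, not procedure-related | excluded: procedure-related |

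The remarks that the lists are non-exhaustive widen the event types within a class. They do not move its time window.

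**Step 2. Do the same for every profile.** A procedure-related event can vary by onset (2 levels), fatal/serious status (3, since a fatal event is always serious), anticipated or not (2), device-related or not (2) and AF-related or not (2).

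- All profiles: 2 × 3 × 2 × 2 × 2 = 48.
- Onset up to day 30: 24, all in the procedure-related class.
- Onset after day 30 and fatal: 8, all in the fatal class.
- Onset after day 30 and non-fatal: 16. The USADE class takes those that are serious, unanticipated and device-related, which is 2 (AF-related or not).
- No class: 16 − 2 = 14. Of these, 2 × 2 × 2 = 8 are anticipated, which is every late, non-fatal, anticipated profile. The other 6 are unanticipated but non-serious or not device-related.

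These are counts of logical combinations, not of events.

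**Step 3. Try the alternative reading.** Suppose the 30-day parenthesis defines what counts as procedure-related. A late event then enters, apart from fatal events and USADE, only if it is AF-related. A late pulmonary vein stenosis that is not called AF-related still has no class. A non-fatal late stroke or embolism caused by the procedure could enter, but only under the not-procedure-related class. The gap remains under both readings.

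**Step 4. Look for another source.**

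- Table 1 records adverse events when they occur. That keeps the form open but adds no class.
- The complications field in the Procedure table belongs to the procedure record.
- The SAP Follow-up table lists admission and discharge dates and hospital stays, with no complication type.
- Vigilance covers device-related events only and is not one of the six SAP tables.
- The remote review in section 11.2 checks the reporting and classification of adverse event data that have been collected. It does not say that further events must be entered.

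**Step 5. See what the analysis can do with events that are entered.** The SAP lists both the procedure date and the adverse event date, so time to onset is event date minus procedure date once the two tables are merged. A split at day 30 can be computed for any event entered. It is not pre-specified.

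**The case against.** A 30-day window for procedural complications is a legitimate registry choice, and section 11.2 prints it openly. That stands. A reader might infer that the limit is hidden, and the documents do not support this. It is missing only from the objective and from the SAP.

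A reader might also infer that attribution to the procedure is lost for good, because section 11.2 asks for relationship to the device and the SAP adverse event list names no relationship variable. This does not follow. An event cannot be placed in the third or fourth class without a judgement on procedure-relatedness, and the SAP lists type of event and type of complications, which may carry it. The SAP list is also not a full inventory of the eCRF, since it omits the device relationship that section 11.2 requires. For events that are entered, attribution may well be recoverable. The problem is confined to events that no class requires, and to late events that could be entered only under a not-procedure-related class.

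Nor do the documents show that late events will be absent. Section 11.2 routes adverse events through the eCRF, the form stays open, and device-related events are to be notified to vigilance as well. Sites may enter them. But entry is then left to the site, and about 30 sites may not decide alike.

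Finally, extending collection yields a limited count. Section 9 adds no tests and section 9.1 schedules an annual follow-up, so late events are those that routine care happens to detect. An amendment after enrollment starts would also leave subjects collected under two rules. Both points stand and shape the fix.

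**Conclusion.** The point holds. As written, section 11.2 gives no class to a non-fatal, anticipated procedure-related event first appearing after day 30. For such events the complications description is in effect a 30-day one, and the objective and SAP do not say so. It is not purely a 30-day description, because late fatal events and USADE are collected.

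The number of events affected cannot be derived from the documents. With about 1000 subjects, each subject whose only complication is missed lowers the proportion by 1/1000 = 0.1 percentage points, but nothing in the plan says how many there would be. A reader might infer a large loss because 30 days is only 30/365 = 8.2% of a year. That is a share of time, not of events. Counting listed event types does not measure the gap either, since both lists are non-exhaustive and the documents do not say which types can appear late.

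The conclusion assumes that sites apply the four classes as written; the eCRF itself is not among the documents. The primary objective is not affected: AF recurrence after the blanking period is named in the after-30-day class and is analysed as efficacy. Severity is minor to moderate.

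**What to change.** In section 11.2, collect procedure-related adverse events to study exit, and class events after day 30 by attribution and not by day.

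In the SAP, tabulate procedure-related complications by onset up to 30 days and after 30 days. Use the procedure and event dates already listed, and take attribution from the event-type variables or from an added relationship-to-procedure field. Describe the late count as events reported in routine practice, not as a complete one-year rate. If the amendment comes after enrollment starts, report which subjects were collected under each rule.

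If collection is not extended, label the result in the SAP as a 30-day complication proportion and list late fatal events and USADE separately.

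The full fix costs a protocol amendment agreed by the sponsor and the Scientific Committee and, if significant, sent to investigators and ethics committees for approval (section 15.5). It also needs a few SAP lines and possibly one eCRF field. The adverse event form is already open throughout follow-up. The downside is a few more event reports and a slightly less favourable complication figure. The label alone needs no change to section 11.2, but it leaves late procedural events undescribed.

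### Section 11.2 has no collection class for a non-fatal, non-USADE event in days 0 to 30 that is judged unrelated to the procedure, so an unrecorded attribution decides whether it enters the data

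*Protocol*

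**What the plan says.** Protocol section 11.2 introduces its list with "The following adverse events will be collected in this registry" and then gives four classes, numbered here for reference:

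1. USADEs. Section 11.1 requires such an event to be serious, caused by or associated with the device, and not already known in kind, severity or frequency from the plan or the product's own documentation.
2. Fatal events: "All adverse events that lead to death".
3. Procedure-related events: "All adverse events related to the procedure (up to 30 days post-procedure), such as (non-exhaustive list". The examples include stroke (under embolic complications), myocardial infarction and bleeding that needs transfusion.
4. AF-related events: "All adverse events related to AF not related to the procedure (that appear after 30 days, throughout the study". The examples, again non-exhaustive, include stroke, systemic embolism, infarction, heart failure and bleeding.

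The same section asks the investigator to judge on the eCRF whether the device may have caused or contributed to an event. It gives no corresponding rule for relatedness to the procedure. The check on reporting is that "All the data collected relating to adverse events will be reviewed remotely to ensure the correct reporting and classification of the event", with the Scientific Committee consulted when there is doubt about classification or relationship with the device.

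Describing procedure-related complications is a secondary objective (section 5.1.2). The variables listed in the SAP section on adverse events include none for relatedness to the procedure or the device.

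**The concern.** Classes 3 and 4 differ in two respects at once: attribution and timing. Class 3 needs a procedure-related event by day 30; class 4 needs an event unrelated to the procedure after day 30. Two combinations are left out. The more important one is the early event judged unrelated, for example a bleed on day 12 put down to anticoagulation.

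In the first month after an ablation it is hardest to separate the procedure from the disease and its treatment. That is when a registry would want attribution recorded next to the event, so that others can re-examine it. Here a judgement of unrelated removes the event from the adverse event data instead of labelling it. With about 30 sites, differences in attribution habit would be mixed with real differences in complications, and no later sensitivity analysis could separate them.

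**Working it through.** The plan states no expected complication rate, so there is no figure to reproduce. The check is a cross-tabulation of the four classes, followed by an illustration on assumed inputs.

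**Cross-tabulation for a non-fatal stroke, embolism, infarction, heart failure episode or bleed**

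| Onset | Judged related to the procedure | Judged unrelated to the procedure |
|---|---|---|
| Days 0 to 30 | Collected (class 3) | No class unless USADE |
| After day 30 | No class unless USADE | Collected if AF-related (class 4) |

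- *Days 0 to 30, unrelated.* Class 2 fails because the event is not fatal, class 3 fails on attribution, and class 4 fails on timing. Class 1 needs device attribution and an event not previously identified. Section 11.2 itself names stroke, infarction and transfusion-requiring bleeding, so an ordinary event of these kinds will rarely qualify.
- *After day 30, related.* This is the mirror gap. A non-fatal pulmonary vein stenosis appearing on day 60 and judged procedure-related is too late for class 3 and excluded from class 4 by its attribution.

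**Do the safeguards reach the empty cells?** The remote review acts on collected data, and the Scientific Committee is consulted on doubts about events under review. Neither sees an event that was never entered.

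**Illustration (assumed inputs).** Take N = 1000, the planned sample size. Let K be the number of eligible non-fatal events in days 0 to 30, and q the share judged procedure-related. Both K and q are assumptions.

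Recorded events = K × q; unrecorded = K × (1 − q); recorded rate = K × q / 1000.

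| K | q | Recorded | Unrecorded | Recorded rate |
|---|---|---|---|---|
| 10 | 0.90 | 9 | 1 | 0.9% |
| 10 | 0.50 | 5 | 5 | 0.5% |
| 20 | 0.90 | 18 | 2 | 1.8% |
| 20 | 0.75 | 15 | 5 | 1.5% |
| 20 | 0.50 | 10 | 10 | 1.0% |
| 30 | 0.90 | 27 | 3 | 2.7% |
| 30 | 0.50 | 15 | 15 | 1.5% |

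For scale, the exact (Clopper-Pearson) 95% interval is 0.48% to 1.83% for 10/1000 and 1.23% to 3.07% for 20/1000. Several of these shifts are within sampling error, but they are systematic and would not shrink with more subjects.

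**Which quantity is affected, and in which direction?** The unrecorded column is an undercount of *all* eligible early events. It is not necessarily an error in the *procedure-related* rate. Suppose K = 20 and 15 are truly procedural. If exactly those 15 are recorded, 15/1000 = 1.5% is correct. If sites call 18 related, the recorded rate is 1.8%, too high. If they call 10 of the 15 related and no others, it is 1.0%, too low. The data cannot show which case applies, because the events judged unrelated were never entered.

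**The case against.** **The brackets may be a timing rule.** The two windows meet at day 30, and stroke, infarction and bleeding appear in both lists. One could read everything up to day 30 as procedural and everything later as AF-related, which leaves no gap. But the protocol states no such rule, and the reading makes the relatedness wording in both classes redundant. The literal reading is stronger. If sites can read it both ways, they will collect differently, which also calls for clearer wording.

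**Other routes exist.** Complications are also a procedure variable (protocol section 9.1 and the SAP's procedure table), hospital stays and admission dates are in the SAP's follow-up table, and device-related events go through vigilance. It would therefore be wrong to say that no trace could remain. The routes are partial, however: vigilance needs a device link, and the follow-up table lists no reason for admission. The broad definition of an adverse event in section 11.1 and the general adverse event row in Table 1 do not override the explicit list in section 11.2.

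**Attribution is part of the objective.** Section 5.1.2 asks for procedure-related complications, so correctly leaving out an unrelated event causes no bias in that rate. This stands. A reader might infer that the 30-day rate can only be biased downwards; the documents do not support that, since over-attribution raises it. Only the count of all such events is necessarily understated.

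**Sinus rhythm disorders.** A reader might infer that sinus dysfunction unrelated to the procedure goes uncollected for 3 months, because one class 4 item reads "atrial flutter or inappropriate sinus tachycardia or sinus dysfunction after the blanking period". That does not follow. The item is an example in a non-exhaustive list, and the class itself covers all AF-related events after day 30.

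**Who judges.** A reader might also infer that the operator's own attribution decides. The documents name the investigator, require a judgement only for the device, and provide review of entered events. What can be said is that nobody is named to judge relatedness to the procedure.

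**Conclusion.** The concern holds as a gap in the collection rules. On the literal wording of section 11.2, whether a non-fatal, non-USADE stroke, embolism, infarction, heart failure episode or bleed in days 0 to 30 enters the adverse event data depends on a judgement of procedure-relatedness that is not itself recorded and has no named assessor. The mirror gap after day 30 arises from the same wording.

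Three consequences follow: the count of all such early events is understated, the 30-day complication description can differ between sites because of attribution habit, and the effect on the procedure-related rate cannot be assessed afterwards.

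The size is unknown. If there were 10 to 30 eligible events and 10% to 50% were judged unrelated, 1 to 15 would go unrecorded; the larger losses need both a high event count and frequent judgements of unrelated, so a modest effect is more likely. The objective affected is secondary and descriptive, and the primary endpoint is not touched. The change is still worth making, because the lost information could not be recovered at analysis.

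**What to change.** - **Days 0 to 30 (protocol section 11.2):** record every event in the listed cardiac, embolic, haemorrhagic, access-site and phrenic categories, whatever the attribution.
- **AF-related class:** open it at the procedure instead of after day 30.
- **After day 30:** add a class for events judged procedure-related, so that late non-fatal, non-USADE complications are collected.
- **Attribution:** add procedure-relatedness as an eCRF field, separate from device-relatedness, and state who judges it.
- **SAP, adverse event section:** add the variable, and report the 30-day rate twice: for all such events, and for those judged procedure-related.

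The cost is a protocol wording change, one eCRF field, one extra SAP table and a few more adverse event forms. No tests or visits are added, and the study remains observational.
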